9.1 Routine adverse event reporting

Adverse event data collection and reporting, which are required as part of every clinical trial are done to ensure the safety of patients enrolled in the studies as well as those who will enroll in future studies using similar agents. Adverse events are reported in a routine manner at scheduled times according to the study calendar in Section 5.0. For this trial, Adverse Event: Baseline, Adverse Event: Solicited and Adverse Event: Other are used for routine AE reporting in Rave.

Attribution of Depression: When reporting depression, the following guidelines should be used for determining attribution to varenicline/placebo:

- If depression existed before the patient started drug, and the severity has not changed, then the event should not be reported as at least possibly related to varenicline/placebo.
- If depression started or worsened after the patient started drug (regardless of smoking status), the event should be reported as at least possibly related to varenicline/placebo.
- If depression starts 7 days or more following cessation of drug, then the event should not be reported as related to varenicline/placebo. because the half-life of the drug is less than 7 days.

Solicited Adverse Events: The following adverse events are considered "expected" and their presence/absence should be solicited, and severity graded, at baseline and at 6, 12, 18 and 24 weeks after surgery.

CTCAE v4.0 Term	CTCAE v4.0 System Organ Class (SOC)
Personality change*	Psychiatric disorders
Suicidal ideation*	Psychiatric disorders

- * Although the black box warning in the prescribing information has been removed (in December, 2016), patients will be monitored for neuropsychiatric events including hostility or changes in behavior or thinking that are not typical for the patient, or for suicidal ideation or suicidal behavior. See Sections 8.2.7 and 8.2.8.

Collection of surgical adverse events: For the purpose of determining the primary endpoint of the study, the following surgical adverse events **must be** collected at 24 weeks after surgery.

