13.1.1 Study Populations

Intent-to-Treat (ITT) Population: Consists of all randomized patients who had surgery. The ITT population will be used for the efficacy evaluation at each of the planned analyses. Following the intent-to-treat principle, patients will be analyzed according to the treatment they were assigned at randomization. Patient with missing values will be considered to have complications.

Safety Population: Consists of all patients who were randomized, had surgery, and who have at least one post-baseline safety assessment. The safety population will be used in the safety data summaries. Note that a patient who had no adverse events (on the Adverse Event CRF) constitutes a safety assessment. Patients who have received at least one dose of study drug but have no post-treatment safety data of any kind would be excluded.

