13.3 Primary analysis

Surgical complication incidence rates at 24 weeks after surgery will be compared between the intervention vs. control groups using a Fisher's exact test.

Logistic regression models will supplement the univariate analysis, using complication incidence as the dependent variable and will include smoking status at the time of surgery as an independent variable and also adjust for age, gender, FTND, time between randomization and surgery, and presence of adjuvant chemotherapy and/or radiation therapy. A separate logistic model will be created including treatment arm instead of smoking status. We will also explore the collinear relationship between arm and smoking status to see whether they can be included together in the logistic models.

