13.6 Power/Sample Size

The primary statistical endpoint for this study is the incidence of surgical complications as described in Sections 13.1 and 13.3. Patients that have any of these individual morbidities will be considered to have a perioperative complication. Patients without any of these individual morbidities will be considered to not have a perioperative complication.

In a study of 635,265 non-cardiac surgical cases treated in 200 centers throughout the United States, the incidence rate of the perioperative complications listed above from the National Surgical Quality Improvement Program (NSQIP) data was in the range of 25–30%. They further found that smokers undergoing non-cardiac surgery had an estimated 40% increased odds of developing major morbidity and mortality within 30 days of surgery over never smokers, representing a modest difference of between 10%-12% in the actual percentage of patients with major morbidity.[90] One report focused on the limitations of NSQIP in identifying adverse events following major cancer surgery. NSQIP does not abstract the complications considered most important by many surgical subspecialists (e.g., anastomotic leak).[91] Therefore, the true impact of smoking on adverse surgical events may be greater in this trial.

For the purposes of this power calculation then, we will assume a 30% perioperative complication incidence rate in the control group.¹⁰⁴ The study design is a randomized clinical trial intended to estimate the incidence rate of perioperative complications in patients who are smoking at the time of enrollment. The primary statistical analysis will be a comparison of the perioperative complication incidence rates from the time of surgery to 24 weeks after surgery between the intervention and control groups. We will hence power the study to detect a 10% difference in perioperative complication rates between the intervention and control groups.

With a sample size of 626 patients (313 patients per arm), a Fisher exact test can detect a difference in the perioperative complication rate between the two treatment groups of 10% (20% versus 30% in the intervention arm and control arm, respectively) with 80% power using a Type I error rate of 5% and a two-sided alternative.

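### Scoring missing primary outcomes as complications is not conservative between the arms, the term is undefined, and no sensitivity analysis tests it

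*Combined protocol and SAP*

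**What the plan says.** Section 13.1.1 defines the analysis set as randomized patients who had surgery, and adds "The ITT population will be used for the efficacy evaluation at each of the planned analyses". Its rule for incomplete outcomes is one sentence: "Patient with missing values will be considered to have complications". It does not say whether a missing value means no post-surgical data at all, a missed week-24 assessment, or one unknown component.

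Section 13.3 applies the test to the filled-in outcome: "Surgical complication incidence rates at 24 weeks after surgery will be compared between the intervention vs. control groups using a Fisher's exact test". The supplementary logistic models use the same dependent variable. The one analysis labelled a sensitivity analysis in Section 13.4 concerns the quality-of-life models.

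On data collection, Section 9.1 introduces its list with "For the purpose of determining the primary endpoint of the study, the following surgical adverse events" and requires collection at 24 weeks after surgery. The calendar in Section 5.0 also marks surgical adverse events at weeks 6, 12 and 18. Under Section 13.2.1, two of the six components (30-day death and 30-day re-hospitalization) are settled before the week-6 visit.

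Section 13.6 sizes the trial at 626 operated patients, 313 in each arm. The complication rates it assumes are "20% versus 30% in the intervention arm and control arm, respectively". The test level is two-sided 5% and the stated power is 80%. The dropout allowance covers only the period before surgery.

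**The concern.** Counting a missing outcome as a failure lowers the apparent performance of a single arm, which is why it is often thought of as cautious. In a comparison of two arms the penalty falls on whichever arm has more missing patients who were in fact free of complications. If that is placebo, the rule creates or enlarges an apparent benefit of varenicline. If it is varenicline, the rule hides a real benefit or suggests harm. The direction is set by follow-up and not by the drug.

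At stake are the type I error and the power of the trial's primary test. Because *missing values* is undefined, the rule may also override information the trial has. On its plain wording, a patient recorded as event-free at weeks 6, 12 and 18 who misses week 24 would be scored as having a complication.

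**Working it through.** **1. The plan's own figure.** Inputs from Section 13.6: 20% v 30%, two-sided 5%, 80% power.

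- Without continuity correction: n = [1.96·√(2·0.25·0.75) + 0.8416·√(0.2·0.8 + 0.3·0.7)]² / 0.10² = (1.2002 + 0.5119)² / 0.01 ≈ 293.2, so 294 per arm.
- With continuity correction: n' = (293.2/4)·[1 + √(1 + 4/(293.2·0.10))]² ≈ 312.8, so 313 per arm and 626 in total. This matches the plan.
- Full enumeration of Fisher's exact test at 313 per arm gives 80.2% power, and an actual type I error of 4.1% at 30% v 30%.

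**2. What the rule does to the rates.** In one arm let p be the true complication rate, m the share missing and r the true risk among the missing. The rate that is tested is

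p + m(1 − r).

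The added difference, placebo minus varenicline, is m_P(1 − r_P) − m_V(1 − r_V). This is the between-arm difference in the share who are both missing and event-free. If missingness is unrelated to outcome, r = p.

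**3. No true effect** (p = 30% in both arms, 313 per arm, exact enumeration). The missing shares are assumptions, because the documents give none for the period after surgery. First, r = 30%:

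| Missing, varenicline v placebo | Rates tested | False difference | Rejection |
|---|---|---|---|
| 5% v 5% | 33.5% v 33.5% | 0 | 4.1% |
| 5% v 6.5% | 33.5% v 34.55% | 1.05 points | 4.9% |
| 5% v 8% | 33.5% v 35.6% | 2.1 points | 7.2% |
| 5% v 10% | 33.5% v 37.0% | 3.5 points | 13.1% |
| 5% v 12% | 33.5% v 38.4% | 4.9 points | 22.4% |

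For scale, 5% v 12% of 313 is about 16 v 38 patients. In the last two rows nearly all rejections favour varenicline. With the arms exchanged, the same figures appear as false harm.

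**4. Missing patients at higher risk** (overall rate still 30% in both arms):

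- r = 60%: 5% v 10% gives 32% v 34%, rejection 7.0%. 5% v 12% gives 32% v 34.8%, rejection 9.9%.
- r = 80%: 5% v 10% gives 31% v 32%, rejection 4.9%. 5% v 12% gives 31% v 32.4%, rejection 5.6%.

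**5. True effect, 20% v 30%,** missingness unrelated to outcome, 10% of varenicline and 5% of placebo patients missing:

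- Varenicline: 0.20 + 0.80·0.10 = 28.0%.
- Placebo: 0.30 + 0.70·0.05 = 33.5%.
- The difference falls from 10 to 5.5 points, and power from 80.2% to 29.1%.

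**The case against.** Several points on the other side have force.

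- **Not every imbalance matters.** A reader might infer that the 5% error rate holds only with identical follow-up. It does not need that. Fisher's test is conservative here, and imbalances up to about 1.5 points (from 5% in the better-followed arm) stay under 5%. Missing patients who truly had complications add no bias. This stands, and it limits the size of the problem.
- **Differential loss is not predicted by the documents.** The trial is double-blind with one calendar for both arms. Patients who stop treatment are still followed (Sections 12.1, 12.2.2 and 12.3). Visits have a 14-day window either way, and weeks 12 and 18 may be done by telephone. Much of the endpoint is settled early or in hospital. All this makes large losses less likely, but it does not change how losses are scored. The telephone option is not listed for week 24, the collection point that Section 9.1 names. The only retention figure in the documents, about 84.5% in another trial of cancer patients (Section 1.1.3), is not given by arm.
- **The loss of event-free data is one reading.** A reader might infer that the plan certainly discards it. *Missing values* could mean no post-surgical outcome data at all, and Section 13.2.1 counts patients without any listed event as free of complications. What the documents support is an undefined term whose plain wording would have that effect.
- **A result driven by follow-up would not be wholly invisible.** Section 13.4 compares completed visits between arms by a rank-sum test, and compares each complication type by arm. The visit comparison covers the treatment phase only, and neither analysis shows how far the primary result depends on the fill-in.
- **Multiple imputation as the primary analysis would be debatable.** It brings its own untestable assumption and has no standard pooling with Fisher's exact test. This stands, so imputation belongs among the sensitivity analyses.

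**Conclusion.** The concern holds in a limited form. The rule is in the current text, governs the primary test, is not conservative between arms and has no planned check. Its effect ranges from negligible (equal loss, or imbalances up to about 1.5 points) to serious: 13.1% rejection at 5% v 10% missing and 22.4% at 5% v 12%, if missing patients carry average risk. At an assumed 60% risk among the missing, 5% v 10% gives 7.0%. In the unfavourable direction, a true 10-point effect can shrink to 5.5 points with 29% power.

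All of these rest on assumed missing rates and on 313 operated patients per arm. They show what the rule can do, not what will happen. The documents do not show that follow-up will differ between arms or in which direction, so they do not support a claim that the rule favours varenicline. The change should be made before unblinding.

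**What to change.** In Section 13.1.1:

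1. Classify the primary endpoint from all surgical adverse event data collected at weeks 6, 12, 18 and 24. Any recorded complication that meets the endpoint definition counts as an event, whatever happens to follow-up later.
2. Limit the missing-equals-complication rule to patients whose status cannot be determined from those data, and state the minimum event-free follow-up that counts as determined.
3. Keep Fisher's exact test as the primary analysis, and report the number of missing outcomes by arm.
4. Prespecify two sensitivity analyses:
   - a tipping-point table that varies the complication rate among missing patients separately in each arm;
   - a multiple-imputation analysis with a logistic model, imputing by arm given the last event-free visit and the Section 13.3 covariates known by the time of surgery (age, gender, FTND score, time from randomization to surgery).

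The cost is revised wording and a little extra programming. No new data or patients are needed.

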5.0 STUDY CALENDAR

Pre-Study Testing Intervals

- To be completed \leq 16 DAYS before registration: History and physical.
- To be completed \leq 6 months before registration: Serum creatinine.

Visit week	Prior to Surgery		Day of Surgery**	Post-Surgery***			
	Prior to Registration†	Baseline*	0	6	12	18	24
Visit #	1	2		3 (A)	4 (A, B)	5 (A, B)	6
Tests and observations							
History & physical (weight, bp, pulse)	E	E		X			X
Height	X						
Serum creatinine	X						
Pregnancy test	C						
Concomitant therapies		X		X	X	X	X
Adverse events		X		X	X	X	X
Surgical adverse events				X(1)	X(1)	X(1)	X(1)
Suicidal ideation monitoring				X (2)	X (2)	X (2)	X (2)
Tobacco use assessment (Appdx IX)	X	X	X	X	X	X	X
Surgical team message		X					
NCI Smoking Quitline		X (3)		X (3)	X (3)		
Sample submission							
Salivary Cotinine Measure		X	X	X	D	D	X
Patient questionnaires							
Contemplation Ladder (Apdx III)	X			X	X		X
SEQ-12 (Apdx IV)		X		X	X		X
FTND (Apdx V)		X					
PHQ-9 (Apdx VI)	X (4)			X	X		X
LASA-12 (Apdx VII)		X			X		X
Was It Worth It Survey (Apdx VIII)					X		X
Drug and Behavioral Support Adherence Logs (Apdx X)		X		X	X		
Correlative study (optional)							
Whole blood	To be collected at baseline, see Sections 6.2 and 14.0.						

† Pre-study testing may be performed on the same day as the baseline visit (see also, Section 7.1).

* Baseline: After randomization and at the time the surgical message is discussed with the cancer patient. If performed within 7 days prior to baseline, the Tobacco Use Assessment need not be repeated.

** Surgery must occur after the TQD defined at baseline and can be performed no sooner than 10 days after randomization and no more than twelve weeks after randomization.

*** Post surgery visits can be +/- 14 days

A Patient-completed booklets for Weeks 12 and 18 should be given to patients at the Week 6 visit. Institutional staff should telephone patients within one week prior to Weeks 12 and 18 to remind them that they will either be completing these booklets by telephone at Weeks 12 and 18 or that they may bring the completed booklet to the clinic when they provide saliva samples for cotinine measurements (see Footnote D).

B May be done by telephone or in person (see footnote D).

C For women of childbearing potential. Must be done within 7 days prior to registration/randomization.

D Patients will be asked to come to the treating institution to provide saliva samples for cotinine measurement. A physician visit is not required.

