7.4 Pharmacologic Intervention (Varenicline)

The initiation of the one-week dose escalation period of varenicline/placebo treatment will be considered Day 1 and the target quit date (one week later) will thus be Day 8 of therapy. Patients will be provided with instructions on the proper use of the medication (i.e., time of day to take the medication).

During Week 1, the dosing will be one of the 0.5 mg varenicline/placebo pills per day for the first 3 days followed by two 0.5 mg pills a day (morning and evening) for the next 4 days.

Weeks 2-12: Day 8 is the target quit day and on this day the patient will take two 0.5 mg pills twice daily (morning and evening). Patients will stay on this dose for 11 weeks.

Agent	Dose	Route	Day	
Varenicline/Placebo	0.5 mg	Oral	Days 1-3	1 pill per day
Varenicline/Placebo	0.5 mg	Oral	Days 4-7	1 pill twice per day – Minimum of 8 hours apart
Varenicline/Placebo	0.5 mg	Oral	Days 8-84	2 pills twice per day – Minimum of 8 hours apart (4 pills per day total)

Dosing should occur with 240 mL of water and it is recommended that patients eat prior to dosing to decrease gastric upset. It is recommended that there be at least 8 hours between the morning and evening dosing. If a dose is missed, the patient should take it as soon as s/he remembers. If it is almost time for the next dose (within 6 hours), the patient should skip the missed dose and take the next one as scheduled. Patients should not take a double dose of varenicline/placebo.

Participating institutions should have a suicide ideation monitoring and response procedures in place. An example of such procedures has been provided in Appendix XI.

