8.2.7 Suicidal ideation: Varenicline is known to cause suicidal ideation, patients must be screened for suicidal ideation at Weeks 6, 12, 18, and 24. If a patient responds with a positive (1+) response to question 9 on the PHQ9, s/he will be evaluated by a physician using the CTCAE.

Any patient with CTCAE grade 2 or higher suicidal ideation will immediately discontinue treatment with varenicline/placebo and be referred to a mental health professional in accordance with institutional guidelines. For reference, the CTCAE grades 1 through 4 for suicidal ideation are provided below:

Grade 1: Increased thoughts of death but no wish to kill oneself

Grade 2: Suicidal ideation with no specific plan or intent

Grade 3: Specific plan to commit suicide without serious intent to die which may not require hospitalization

Grade 4: Specific plan to commit suicide with serious intent to die which requires hospitalization

8.2.8 Personality Change: Any patient with CTCAE grade 3 or greater personality change will discontinue treatment with varenicline/placebo and be referred to a mental health professional in accordance with institutional guidelines. For reference, the CTCAE grades 1 through 4 for personality change are provided below:

Grade 1: Mild personality change

Grade 2: Moderate personality change

Grade 3: Severe personality change; hospitalization not indicated

Grade 4: Life-threatening consequences, threats of harm to self or others; hospitalization indicated

8.2.9 Somnambulism: Any patient experiencing sleep walking will discontinue treatment with varenicline.

8.2.10 Pregnancy: Varenicline/placebo will be immediately permanently discontinued for any patient who becomes pregnant during the treatment period of the study.

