9.2 CTCAE Routine Reporting Requirements

In addition to the solicited adverse events listed in Section 9.1, the following table outlines the combinations of time points, grades and attributions of AEs that require routine reporting to the Alliance Statistics and Data Center. Questions about routine reporting should be directed to the Data Manager.

Combinations of CTCAE Grade & Attribution Required for Routine AE Data Submission on Case Report Forms (CRFs)

Attribution	Grade 1	Grade 2	Grade 3	Grade 4	Grade 5
Unrelated			a	a	a
Unlikely			a	a	a
Possible		a	a, b	a, b	a, b
Probable		a	a, b	a, b	a, b
Definite		a	a, b	a, b	a, b

- a) Adverse Events: Other CRF - Applies to AEs occurring between registration and within 30 days of the patient's last treatment date, or as part of the Clinical Follow-Up Phase.
- b) Adverse Events: Late CRF - Applies to AEs occurring greater than 30 days after the patient's last treatment date.

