12.2.2 Follow-up for Patients Never Receiving Protocol Intervention

Study participants who receive the study intervention (varenicline/placebo and behavioral module), but never go on to have the surgery, can complete study intervention if they wish. Data on outcome and complications (adverse events) will continue to be collected, but these patients will not be included in the analysis of the primary endpoint.

Study participants initiate the study intervention (varenicline/placebo and behavioral module), go on to receive surgery, but wish to stop study intervention thereafter, will continue to have data on outcome and complications (adverse events) collected. These data will be used in the analysis of the primary endpoint.

Study participants who were registered/randomized but never received varenicline/placebo will be considered “canceled” and baseline data must be submitted per Section 5.0..

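### The Safety Population in Section 13.1.1 requires surgery, so adverse events collected from patients who took study drug but were never operated on belong to no planned safety summary

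*Combined protocol and SAP*

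**What the plan says.** Section 13.1.1 gives the Safety Population three conditions: "Consists of all patients who were randomized, had surgery, and who have at least one post-baseline safety assessment". It assigns this set to the safety data summaries and names no other. Dosing appears only in the closing sentence, as a reason for leaving patients out: "Patients who have received at least one dose of study drug but have no post-treatment safety data of any kind would be excluded".

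Drug comes before surgery. Section 7.3 hands over the full supply after the baseline visit. Section 7.4 says that "the target quit date (one week later) will thus be Day 8 of therapy", and Section 5.0 adds: "Surgery must occur after the TQD defined at baseline".

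Section 12.2.2 covers participants who receive varenicline/placebo "but never go on to have the surgery, can complete study intervention if they wish". Of their data on outcome it says: "complications (adverse events) will continue to be collected, but these patients will not be included in the analysis of the primary endpoint". It is silent on safety summaries. Participants who never received drug are treated there as cancelled, and only baseline data are requested.

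Section 9.2 states no surgery condition for routine reporting. One form "Applies to AEs occurring between registration and within 30 days of the" last treatment date, or during clinical follow-up. A second, for late events, covers what happens more than 30 days after the last treatment date.

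**The concern.** Adverse effects of a drug can occur in anyone who takes it, and here everyone on schedule takes it before surgery. A safety set that requires surgery drops exposed patients because of something that happens after randomization and after first dose. If drug effects, or anything else that differs by arm, influence who reaches surgery, the summaries by arm describe a selected group. The documents give neither the reasons for dropout before surgery nor its split by arm, so neither direction nor size can be inferred.

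There is also a plain loss of information. Adverse events in these patients are collected under Sections 9.2 and 12.2.2, yet a programmer following Section 13.1.1 would leave them out of every safety summary. What is at stake is how complete and interpretable those summaries are.

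**Working it through.** **1. Reproduce the plan's enrollment figure.** Inputs from Section 13.6: 626 operated patients and at most 20% dropout before surgery. 626 / (1 − 0.20) = 782.5, rounded up to 783. This matches.

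**2. Enrolled patients expected without surgery.**
- Main plan: 783 − 626 = 157, and 157/783 = 20.1%.
- Early accrual stop at 700 (Section 13.7, if at most 10% fail to have surgery): 0.10 × 700 = 70 at the trigger rate, or 700 − 626 = 74 (74/700 = 10.6%) if exactly 626 are operated on.

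**3. How many of these took drug.** The documents do not say, so the dosed share is an assumption, shown over its whole range for the main plan:

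| Assumed dosed share of the 157 | Dosed, never operated on |
|---|---|
| 0% | 0 |
| 25% | about 39 |
| 50% | about 78 |
| 75% | about 118 |
| 100% | 157 |

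In the 700 case the range is 0 to 74. If every operated patient is dosed and every patient counted has a post-baseline assessment, the safety denominator moves from 626 to somewhere between 626 and 783.

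**4. Exposure before surgery.** The target quit date is Day 8 of therapy and surgery follows it, so on schedule Days 1 to 7, at least 7 days of drug, come first.

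**5. When adverse events are first assessed on schedule.** After baseline, Sections 5.0 and 9.1 time every adverse event assessment from surgery, the first at week 6 (42 days). Section 7.3 puts the target quit date at least 10 days after randomization, so surgery is on day 11 at the earliest. The latest is 12 weeks, or day 84.
- First visit: 11 + 42 = 53 to 84 + 42 = 126 days after randomization.
- With the 14-day window: 53 − 14 = 39 to 126 + 14 = 140 days.

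A patient without surgery has no dated adverse event visit after baseline.

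**6. Would a cut-off 30 days after last dose be harmless in a dose-based set?** It would not.
- The last scheduled dose is on Day 84 (Section 7.4), so the window closes at 84 + 30 = Day 114.
- Surgery is on Day 9 of therapy at the earliest. Week 18 is then 9 + 126 = Day 135, or Day 121 with the window.
- Week 24 is 9 + 168 = Day 177, or Day 163 with the window.

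Every week 18 and week 24 assessment falls outside. Section 9.1 solicits personality change and suicidal ideation at those visits, and Section 8.2.7 says that "patients must be screened for suicidal ideation at Weeks 6, 12, 18, and 24".

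**The case against.** The best defence is that surgery defines this trial. The intent-to-treat set also requires it, and every scheduled adverse event visit after baseline is timed from it, so the operated patients form the one uniformly assessed group. Section 13.1.1 plans summaries and no formal comparison of drug adverse events between arms, and safety is not a listed objective or endpoint. A supplementary listing for dosed, unoperated patients might then be enough.

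Much of this stands and limits the point. The analogy with the intent-to-treat set does not carry over: surgical complications can occur only after surgery, while drug effects do not depend on it. Uneven ascertainment is a reason to show unoperated patients separately and to say why, but not to leave out events already collected. A listing would help, but the safety set would still be defined by surgery.

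Some stronger readings are tempting, and the documents do not support them.
- *Participants are less protected.* Expedited reporting (Section 9.3), the stopping rule (Section 13.9) and the six-monthly monitoring board reports (Section 13.8) state no surgery condition. That the stopping rule counts treated or enrolled patients is not an error either, since it is a running trigger and need not share a denominator with the summaries.
- *Sections 12.2.2 and 13.1.1 contradict each other.* Section 12.2.2 says nothing about safety summaries. The data are unassigned, which is a gap.
- *157 exposed patients are omitted.* That figure counts enrolled patients without surgery, dosed or not.
- *Operated patients who never took drug will enter the set.* They are treated as cancelled with baseline data only, so few would have the post-baseline assessment that Section 13.1.1 requires.

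**Conclusion.** The point holds as a gap in Section 13.1.1. As written, the safety summaries omit exposed patients whose adverse events the protocol collects. The size is 0 to 157 patients on the main planning figures, or 0 to 74 if accrual stops at 700. Both ranges rest on the expected surgery rates in Sections 13.6 and 13.7 and on an unknown dosed share. The summaries by arm are conditioned on an event after randomization and first dose, and any resulting bias has unknown direction and size. It is worth correcting because the remedy is a small edit to the text.

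**What to change.** In Section 13.1.1:
- Replace the surgery condition with having taken at least one dose of varenicline/placebo. Keep the condition of at least one post-baseline safety assessment, and report by arm how many dosed patients have no post-baseline safety data.
- Summarize all adverse events already required by Sections 9.1 and 9.2, including the week 18 and week 24 solicited assessments and the late events. Do not cut off at 30 days after last dose; events up to and after that point may be shown separately.
- Tabulate surgical adverse events in operated patients only, and show drug adverse events by surgery status.
- State that ascertainment in unoperated patients rests mainly on routine reporting, because scheduled visits are timed from surgery, and so is not comparable with that in operated patients.

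The cost is a text edit and one extra display, since routine reporting for these patients is already required. The real drawback is the uneven ascertainment. Removing it would need a change to the study calendar, which this fix does not require. Sample size, power and the primary analysis are untouched.
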